6.3.4 Safety Related Laboratory Assessments

A central laboratory will be utilized to perform safety related clinical laboratory assessments as specified in Table 1 and Table 2 and as described in this section. Samples for laboratory assessments performed at Baseline must be collected **prior to study drug dosing**. The Investigator or qualified designee must review the results of all central laboratory testing to assess subject eligibility at Screening and Baseline, as well as continued study participation for the duration of the Double-Blind Treatment Period. Procedures for sample collection and handling, including the blinded reporting of any results, will be detailed in the central laboratory manual and/or SPM.

In addition to standard serum chemistry, lipid, hematology, and coagulation panels (see Table 2) conducted at specific visits throughout the study, samples to assess HIV and Hepatitis B/C, G6PD, and recreational drug use will only be collected at Screening to determine those factors that could render the subject unsuitable for the study or confound study results.

A local laboratory will perform serum pregnancy testing at Screening, Baseline, and at the Week 18 visit for all FOCP. A locally performed urine pregnancy test will also be done at Baseline. A local laboratory will perform FSH testing at Screening for all postmenopausal females.

6.3.5 Adverse Events

Adverse events will be collected from the time at which the potential subject signs the ICF. Subjects will be instructed to report all AEs during the study and will be assessed for the occurrence of AEs throughout the study until at least 30 days after discontinuing the study drug. General and non-leading questions such as "How are you feeling?" should be asked when assessing the occurrence of AEs. The definition, reporting, and recording requirements for AEs are described in Section 7.0.

6.3.6 Prior and Concomitant Medications

Prior and concomitant medications will be reviewed to determine study eligibility for potential subjects and to monitor continued study participation. In addition to medication history (see Section 6.1.1), any medication, including prescription, over-the-counter, or natural/herbal preparations, received within 28 days of

Clinical Protocol

randomization and the first dose of study drug through at least 30 days after discontinuing the study drug must be recorded in the eCRF. Changes to medication doses or regimens, e.g., in response to an AE, must also be recorded in the eCRF. See Sections 4.5 and 4.6 for details on non-prohibited and prohibited medications.

7.0 PROCEDURES FOR HANDLING ADVERSE EVENTS AND SERIOUS ADVERSE EVENTS

7.1 DEFINITION OF AN ADVERSE EVENT

The following definition of an AE will be used for this study: Adverse event means any untoward medical occurrence associated with the use of a drug in humans, whether or not considered drug related.

An AE can be any unfavorable and unintended sign (including an abnormal laboratory finding), symptom, or disease (new or exacerbated) temporally associated with the use of the investigational product, regardless of whether it is considered to be related to the investigational product.

The following are examples of AEs:

- Significant or unexpected worsening or exacerbation of the indication under study.
- Exacerbation of a chronic or intermittent preexisting condition, including an increase in frequency or intensity of the condition.
- New conditions detected or diagnosed after investigational product administration, even if they were present before the start of the study.
- Signs, symptoms, or the clinical sequelae of a suspected interaction with another medical product.
- Signs, symptoms, or the clinical sequelae of a suspected overdose of either investigational product or a concurrent medication.

Overdose should not be reported as an AE or serious adverse event (SAE), but rather the symptoms resulting from the overdose should be reported as such.

Examples of AEs do not include the following:

• Medical or surgical procedures (e.g., endoscopy, appendectomy). The medical condition that led to the procedure as the AE should be reported.

- Situations that are unwanted by the subject but in which an untoward medical occurrence did not occur, for example social inconvenience after admission to a hospital.
- Anticipated day-to-day fluctuations of a pre-existing disease or condition (present or detected before enrollment) that does not worsen overall.
- Expected progression of the disease being studied, including signs or symptoms of the disease, unless progression is more severe than expected for the subject's condition.

Adverse events may include pre-treatment or post-treatment events that occur as a result of protocol-mandated procedures (e.g., invasive procedures, modification of the subject's previous therapeutic regimen).

Adverse events should be captured even if they occur during periods without drug treatment, post-treatment periods, known placebo treatment, or in a reference or control group receiving drug or nondrug therapy.

The Investigator is responsible for all AE assessments. The Investigator and investigational site staff will note all AEs mentioned by the subject at Baseline and during study drug administration. All clinical complaints volunteered by or elicited from the subject during the study will be recorded on the appropriate page of the eCRF for the study period indicated (see Section 6.3.5). The subject will receive appropriate treatment and medical supervision for any AE that occurs.

All AEs judged to be clinically significant, including clinically significant laboratory abnormalities, will be followed until resolution. All AEs will be summarized in the annual report or more frequently if requested by the regulatory agency. Serious adverse events require special reporting in addition to documentation in the eCRF as described in Section 7.7.

7.2 DEFINITION OF A SERIOUS ADVERSE EVENT

In this study, an SAE is defined as an AE that meets any of the following criteria:

- Results in death.
- Is life-threatening. The term life-threatening in the definition of an SAE refers to an event in which the subject was at risk of death at the time of the event. The term life-threatening does not refer to an event that, had it occurred in a more severe form, might have caused death.
- Requires hospitalization or a prolongation of an existing hospitalization. In general, hospitalization signifies that the subject has been detained at the hospital or emergency ward for observation or treatment that would not have been appropriate in the physician's office or out-patient setting. Complications that occur during hospitalization are AEs, but not necessarily SAEs. A medical occurrence or complication that prolongs hospitalization is an SAE. When there is doubt as to whether hospitalization occurred or was necessary, the AE should be considered an SAE. Hospitalization for elective treatments of a preexisting condition that did not worsen from its original Baseline level is not considered an SAE.
- A persistent or significant incapacity or substantial disruption of the ability to conduct normal life functions. This does not include AEs of relatively minor medical significance such as uncomplicated headache, nausea, vomiting, diarrhea, influenza and accidental trauma (e.g., sprained ankle) that may interfere or prevent everyday life functions but do not constitute a substantial disruption.
- A congenital anomaly or birth defect. This refers to the offspring of a study subject.
- An other important medical event. Medical or scientific judgment should be exercised when deciding whether reporting is appropriate for other important medical events that may not result in death, be life-threatening, or require hospitalization but still may jeopardize the subject or may require medical intervention to prevent one of the outcomes listed in this definition. These events should also be considered serious. Examples of such events are intensive treatment in an emergency room or at home for allergic bronchospasm, blood

dyscrasias, or convulsions that do not result in hospitalization or in the development of drug dependency or drug abuse.

An SAE requires additional detailed reports and follow-up. The content of these detailed reports must address the Investigator's estimate of causality. The Medical Monitor will review the SAE to determine if it is an expected SAE (i.e., whether or not the SAE is identified in nature, severity, and frequency in the Investigator's Brochure).

7.3 RECORDING ADVERSE EVENTS AND SERIOUS ADVERSE EVENTS

When an AE or SAE occurs, the Investigator is responsible for reviewing all documentation (e.g., hospital progress notes, laboratory, and diagnostic reports) relative to the event(s). The Investigator will record all relevant information about any AE (including SAEs) on the AE page of the eCRF. It is not acceptable for the Investigator to send photocopies of the subject's medical records in lieu of the properly completed AE or SAE pages of the eCRF. These documents should not be sent unless they are specifically requested by the Sponsor's or designee's pharmacovigilance department. If this request occurs, all subject identifiers and protected health information should be blinded on the copies of the medical records before submission to the pharmacovigilance department and to the appropriate authorities.

The Investigator will also attempt to report a diagnosis, instead of signs, symptoms, or other clinical information, for the AE. The diagnosis, not the individual signs and symptoms, should be documented on the appropriate page of the eCRF as the AE or SAE. In addition, SAEs need to be reported in the SAE report. Adverse events being processed as SAEs will also require additional documentation. The SPM (or other applicable instructions) provides additional guidelines about reporting SAEs.

7.4 ASSESSMENT OF INTENSITY

The Investigator will assess the intensity for each AE and SAE reported during the study on the basis of his or her clinical judgment. The classifications in Table 5 should be used in assigning intensity of each AE recorded in the eCRF.

Table 5. Classification of AEs by Intensity

| Intensitya | Definition | |
|--|--|--|
| Mild AE (Grade 1) | An event that is easily tolerated by the subject, causing minimal discomfort and not interfering with everyday activities | |
| Moderate AE (Grade 2) | An event that is sufficiently discomforting to the extent of interfering with normal everyday activities | |
| Severe AE (Grade 3) | An event that prevents the subject from performing normal everyday activities | |
| Life-threatening or disabling AE (Grade 4) | An event that, at the time of occurrence, put the subject at risk of death or resulted in a persistent or significantly disability or incapacity | |
| Death related to AE (Grade 5) | An event that resulted in death | |

^a From Common Terminology Criteria for Adverse Events, Version 4.0

Any AE that changes in intensity or grade during a single occurrence of an AE will be recorded in the eCRF at the highest level experienced by the subject.

An AE that is assessed as severe should not be confused with an SAE. Severity is a category used for rating the intensity of an AE (such as mild, moderate, or severe myocardial infarction). However, an AE itself may be of relatively minor medical significance, such as a severe headache. Both AEs and SAEs can be assessed as severe. An AE is considered serious when it meets one of the predefined outcomes described in Section 7.2.

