7.9 LIVER ADVERSE EVENTS

The algorithm (Chalasani and Regev 2016) described in Table 8 will be used to monitor for drug-induced liver injury (DILI).

Table 8. Algorithm to Monitor for DILI

| Treatment Emergent ALT | Treatment Emergent Total Bilirubin (TB) | Liver Symptoms | Actions |
|--|--|----------------|---|
| Normal Baseline: ALT >2x ULN | Normal | None | Repeat ALT, AST, ALP, TB, in 2-5 days after receipt of the scheduled ALT results (Table 1). |
| Elevated Baseline: ALT >2x Baseline or >300 U/L (whichever occurs first) | Patients with Gilbert's syndrome: No change in Baseline TB | None | Follow up for symptoms. |

| Treatment Emergent ALT | Treatment Emergent Total Bilirubin (TB) | Liver Symptoms | Actions |
|---|--|---|---|
| Normal Baseline: ALT >5x ULN | Normal | None | Interrupt study drug. Initiate close monitoring and workup for competing etiologies. |
| Elevated Baseline: ALT >5x Baseline or >500 U/L (whichever occurs first) | Patients with Gilbert's syndrome: No change in Baseline TB | | Study drug can be restarted only if another etiology is identified and liver enzymes return to baseline. |
| Normal Baseline: ALT >2x ULN | TB >2x ULN | None | Interrupt study drug. Initiate close monitoring and workup for competing |
| Elevated Baseline: ALT >2x Baseline or >300 U/L (whichever occurs first) | Patients with Gilbert's syndrome: Doubling of direct bilirubin | | etiologies. Study drug can be restarted only if another etiology is identified and liver enzymes return to baseline. |
| Normal Baseline: ALT >2x ULN | Normal or elevated | Severe fatigue, nausea, vomiting, right upper quadrant pain | Interrupt study drug. Initiate close monitoring and workup for competing |
| Elevated Baseline: ALT >2x baseline or >300 U/L (whichever occurs first) | - | | etiologies. • Study drug can be restarted only if another etiology is identified and liver enzymes return to baseline. |

Note: Baseline is the average of the Screening and Baseline visit ALT measurements.

As described in Table 8, close monitoring of the subject must be initiated if certain signals of a possible DILI are detected. At a minimum, close monitoring includes:

- Repeating liver enzyme and serum bilirubin tests 2-3 times weekly. The frequency of retesting can decrease to once a week or less if abnormalities stabilize or if the study drug has been discontinued and the subject is asymptomatic.
- Obtaining a more detailed history of the subject's symptoms and prior or concurrent diseases.

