8.4 PREMATURE STUDY OR SITE TERMINATION

If the Sponsor, Investigator, Medical Monitor, Study Monitor, and/or appropriate regulatory officials discover conditions arising during the study that indicate that the study should be halted or that the investigational site should be terminated, this action may be taken after appropriate consultation among the Sponsor, Investigator, Medical Monitor, and/or Study Monitor. The Common Terminology Criteria for Adverse Events (CTCAE), Version 4.0, will be used for assessment of trial stopping criteria.

The study will be stopped if:

- Three patients develop the same Grade 3 CTCAE, or
- Two patients develop any Grade 4 CTCAE, or
- One patient develops a Grade 5 CTCAE.

Additional conditions that may warrant termination of the study include, but are not limited to, the following:

- The discovery of an unexpected, serious, or unacceptable risk to the subjects enrolled in the study;
- A decision on the part of the Sponsor to suspend or discontinue testing, evaluation, or development of the investigational product.

A study conducted at a single investigational site in a multicenter study may also warrant termination under the following conditions:

- Failure of the Investigator to enroll subjects into the study at an acceptable rate;
- Failure of the Investigator to comply with pertinent regulations of appropriate regulatory authorities;
- Submission of knowingly false information from the investigational site to the Sponsor, Study Monitor, or appropriate regulatory authority;
- Insufficient adherence to protocol requirements.

Clinical Protocol

Study termination and follow-up will comply with conditions set forth in ICH E6, Guideline for Good Clinical Practice (GCP), Sections 4.12, 4.13, 5.20, and 5.21.

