5.3. SAFETY

5.3.1. Adverse Events

AEs will be mapped to a Medical Dictionary for Regulatory Activities (MedDRA) version 20.1 preferred term (PT) and system organ classification (SOC). If a subject experiences multiple events that map to a single preferred term, the greatest severity grade according to the Common Terminology Criteria for Adverse Events (CTCAE) Version 4.0, and strongest investigator assessment of relation to study medication will be assigned to the preferred term for the appropriate summaries. Should an event have a missing severity or relationship, it will be classified as having the highest severity and/or strongest relationship to study medication. The occurrence of TEAEs will be summarized by treatment group by SOC, PT, and severity. Separate summaries of treatment-emergent serious adverse events (SAEs), TEAEs related to study drug, severe or life-threatening TEAEs, and TEAEs leading to the discontinuation of study treatment will be generated. Additionally, the occurrence of liver-specific AEs will be summarized by treatment group. All adverse events reported will be listed for individual subjects showing verbatim term, PT and SOC. All AEs that occurred prior to the initiation of study treatment will be excluded from the tables but will be included in the listings.

Missing onset dates will be imputed as previously outlined in Section 3.3.5 as required to determine treatment-emergent events.

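### Table 5 grades a symptom-free laboratory event as mild even when Table 8 requires study-drug interruption, and Section 8.4 does not say which grade it counts

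*Protocol*

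**What the plan says.** Protocol 7.4 on recording intensity: "The classifications in Table 5 should be used in assigning intensity of each AE recorded in the eCRF". The investigator applies the table by clinical judgment, and its footnote gives CTCAE v4.0 as the source. The definitions are:

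- Grade 1: "An event that is easily tolerated by the subject, causing minimal discomfort and not interfering with everyday activities"
- Grade 2: "An event that is sufficiently discomforting to the extent of interfering with normal everyday activities"
- Grade 3: "An event that prevents the subject from performing normal everyday activities"
- Grade 4: an event that "put the subject at risk of death or resulted in a persistent or significantly disability or incapacity"
- Grade 5: death.

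Protocol 7.1 includes abnormal laboratory findings in the definition of an adverse event.

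Protocol 7.9, Table 8, has four tiers. Three list no liver symptoms, and two of those three carry the action "Interrupt study drug. Initiate close monitoring and workup for competing etiologies".

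Protocol 8.4: "The Common Terminology Criteria for Adverse Events (CTCAE), Version 4.0, will be used for assessment of trial stopping criteria". The study stops if three patients have the same Grade 3 event, two have any Grade 4 event, or one has a Grade 5 event.

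SAP 5.3.1 assigns to each preferred term "the greatest severity grade according to the Common Terminology Criteria for Adverse Events (CTCAE) Version 4.0". It plans a summary by severity (Table 14.3.1.2) and a separate summary of severe or life-threatening treatment-emergent events.

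**The concern.** In a liver trial, the event of most interest may be a laboratory finding that the subject does not feel. Table 5 has no place for it above Grade 1 unless the investigator judges that it put the subject at risk of death or caused disability. The plan therefore takes such an event seriously enough to interrupt study drug, and at the same time gives sites definitions that label it mild.

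Two outputs depend on that label. The SAP severity tables would show drug-interrupting enzyme rises alongside trivial complaints. The grade counts in 8.4 might or might not see these events, because the protocol does not say which grade they use. A site that follows Table 5 to the letter and one that takes the footnote as a pointer to CTCAE itself could also grade the same event differently. That last risk follows from the wording; the documents do not show that it has happened.

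**Working it through.** The plan states no figure on this point, so the check sets the passages side by side.

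**Step 1. Which symptom-free tiers interrupt drug (Protocol 7.9, Table 8)**

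| ALT trigger | Total bilirubin | Liver symptoms | Study drug interrupted? |
|---|---|---|---|
| >2x ULN; if baseline elevated, >2x Baseline or >300 U/L | Normal | None | No (repeat tests, follow up) |
| >5x ULN; if baseline elevated, >5x Baseline or >500 U/L | Normal | None | Yes |
| >2x ULN; if baseline elevated, >2x Baseline or >300 U/L | >2x ULN | None | Yes |
| >2x ULN; if baseline elevated, >2x Baseline or >300 U/L | Normal or elevated | Present | Yes |

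The table omits the separate bilirubin criteria for Gilbert's syndrome. Two tiers, the second and third, are symptom-free and interrupt drug.

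**Step 2. Apply Table 5 to those two tiers**

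- Grade 2 needs discomfort that interferes with activities: not met without symptoms.
- Grade 3 needs activities to be prevented: not met.
- Grade 1 (tolerated, minimal discomfort, no interference): met.
- Grade 4 (risk of death or disability): open to judgment. An investigator could argue for it where ALT and bilirubin are both raised. It is harder to argue for ALT alone with normal bilirubin, so the ALT >5x tier is the clean example.

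**Step 3. Follow the grade into the SAP**

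The Table 5 grade is the only one the protocol tells sites to record. SAP 5.3.1 summarises a grade that it attributes to CTCAE v4.0. If the recorded grade is what is tabulated, the ALT-only event is Grade 1 in Table 14.3.1.2 and missing from the summary of severe or life-threatening events.

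**Step 4. Follow the grade into Protocol 8.4**

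Section 8.4 names CTCAE v4.0 but refers neither to Table 5 nor to the eCRF grade. There are two readings:

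- It reads the Table 5 grade. An event recorded as Grade 1 then adds nothing to the Grade 3 count, however many subjects have it. On the same reading, three severe headaches would meet the rule, although 7.4 itself uses a severe headache as an example of an event of minor medical significance.
- It reads CTCAE directly. The grade used for stopping may then differ from the recorded one. By how much cannot be shown, because neither document reproduces the CTCAE laboratory criteria.

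**Step 5. Why the choice of reading could matter (illustration only)**

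The documents give no event rate. Assume a true rate p for such events, independence between subjects, N = 117 (Protocol 3.3), and that each event counted as Grade 3. Then

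P(at least 3) = 1 − Σ over k = 0, 1, 2 of C(117, k) p^k (1 − p)^(117 − k).

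At p = 1% the three terms are about 0.309, 0.365 and 0.214, so P = 1 − 0.887 = 11.3%.

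| Assumed p | P(at least 3 of 117) |
|---|---|
| 0.5% | 2.1% |
| 1% | 11.3% |
| 2% | 41.5% |
| 3% | 68.5% |
| 5% | 93.6% |

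Both the rates and the Grade 3 assignment are assumptions. The table shows only that the two readings can give different results; the finding does not rest on it.

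**The case against.** The strongest reply is that Table 5, Section 8.4 and the SAP all cite the same CTCAE version, so on their face there is one scale. To show that CTCAE would grade an ALT rise differently, one needs thresholds that the documents do not contain. That stands, and no claim is made here about the grade CTCAE would give. It does not remove the mismatch between Table 5 and Table 8, which is visible in the protocol alone. The footnote may even strengthen it, by telling sites that the activity-based definitions already are the CTCAE grading.

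The second reply is that liver signals are handled outside the grade. This is largely right. Table 8 acts on laboratory values whatever the grade. The Medical Monitor should be consulted on possible drug-induced liver injury. An event can be serious regardless of intensity, and 8.4 separately allows termination for unacceptable risk. A DSMB oversees safety. The SAP summarises liver-specific events and, in 5.3.2, tabulates ALT above 123 U/L and total bilirubin above 2.00 mg/dL by arm. Those tables use one cut-off per parameter, so they show neither the >5x tier nor the combined ALT and bilirubin tier, and nothing says that they feed 8.4.

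A reader might infer three stronger points that the documents do not support:

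- That no such event can exceed Grade 1. Grade 4 does not depend on everyday activities, and grading is by judgment.
- That these events can never count towards stopping. This holds only for the Grade 3 count, and only if 8.4 reads the Table 5 grade, which it does not say.
- That all three symptom-free tiers are affected alike. The first does not interrupt drug.

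**Conclusion.** The point holds in a limited form. Followed as written, Table 5 gives Grade 1 to a symptom-free ALT rise in the >5x tier that requires drug interruption, and the SAP then reports that event as mild under a CTCAE v4.0 label. This assumes that the investigator applies the definitions literally and that the SAP tabulates the recorded grade. The tier with raised bilirubin is less certain, because Grade 4 is arguable there.

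For 8.4 the conclusion is that the rule is unclear, not that it fails: it counts grades without naming their source. The reach is the adverse-event severity tables and possibly the grade-count limbs of 8.4. The liver signal itself is not lost. The point deserves correction because a stated rule gives a poor result in the organ under study and the remedy is cheap.

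**What to change.** Reconcile Protocol 7.4, 7.9 and 8.4 with SAP 5.3.1:

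1. State one grading scale for laboratory adverse events that does not depend on everyday-activity wording.
2. Record that grade in the eCRF and use it in the SAP severity tables.
3. State which grade 8.4 reads, and whether Table 8 events count there.

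The laboratory thresholds and the way the stopping rule operates are for the sponsor to decide; none is proposed here. The cost is protocol and SAP wording plus an eCRF completion guideline. No new assessments are needed.
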